10.2 Planned statistical methods

10.2.1 Overview

A statistical analysis plan (SAP) describing the detailed statistical analysis will be provided as a separate signed document.

The statistical analysis will consist of reporting of individual data listings, providing descriptive statistics and graphs for all parameters of interest, and applying the statistical test of the primary analysis.

10.2.2 Descriptive analysis

10.2.2.1 Patient characteristics:

1. Age
2. Ethnic origin
3. Country
4. Medical/surgical history including pre-treatment events
5. Previous and concomitant medication
6. Histological data: proportions of unilateral and bilateral disease, number of cores involved
7. Morphometric data: prostate volume

10.2.2.2 Treatment modalities:

1. Number of fibers and energy applied
2. LDI achieved
3. Adherence to treatment guidance and reasons for changes

10.2.2.3 Descriptive statistics

Descriptive statistics (number, mean, standard deviation, median, quartiles, minimum and maximum) will be calculated for quantitative variables; frequency counts and cumulative frequencies (if appropriate) by category will be given for qualitative variables. For measurements that are repeated over time (e.g. PROMs and QoL), descriptive statistics will be provided at all measurement times and summary statistics will be plotted over time. Two-sided 95%-confidence intervals will be given where appropriate. These intervals will be two-sided and will have 95% coverage.

10.2.2.4 Intention-to-treat, per protocol and safety populations

All descriptive statistics will be shown on all patients enrolled in this study, for whom CRF at entries are available irrespective of protocol deviations (**intention-to-treat population**). Safety data will be analyzed using all patients who have received any amount of TOOKAD® Soluble or have started any part of the VTP procedure, including anesthesia (**safety population**).

Descriptive statistics will also be shown using all patients who comply with the study protocol (**per-protocol population**). The per protocol population of efficacy will consist of all patients who:

1. complied with the protocol for inclusion criteria and exclusion and follow-up,

2. received the appropriate dose of TOOKAD® Soluble, LDI and energy delivered and underwent the VTP procedure, receiving the ascribed dose of TOOKAD® Soluble and light,
3. had no major protocol deviations.

10.2.2.5 Drop-outs and censored patients

All subjects who withdraw from the trial before the VTP procedure will be considered as drop-outs. Every effort will be made to minimize dropouts.

Eligible subjects who undergo additional radical therapy (surgery or radiation) after the VTP procedure or receive medical therapies (hormone or chemotherapies) will be kept in the intention to treat population but will be excluded from the per protocol population.

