5.5 End of study

5.5.1 Study Completion Procedures

Subjects will be considered to have completed the study when they have completed all examinations up to and including the Month 60 visit.

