6.4.11 Post-procedure or follow-up assessments

Based on the results of post-procedure or follow-up assessments, or upon decision by them or their clinician, patients may at any time decide to undergo additional radical therapy.

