10.3 Analysis of primary endpoint

The primary efficacy variable is the result of the Month 12 biopsy, in which success is defined by absence of detectable Gleason grade 4 or 5 prostate cancer in any given biopsy.

The primary endpoint will be analysed as a dichotomous outcome, i.e., success (absence of any histology result positive for Gleason 4 or 5 prostate cancer at 12 months) or failure (presence of at least one result positive for Gleason grade 4 or 5 prostate cancer at 12 months).

A descriptive analysis of the month-3 biopsies will be conducted.

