### **Primary efficacy analysis**

The proportion of patients with no pattern 4 or 5 found in the 12 month biopsy will be reported along with a one-sided 90% confidence interval. Patients who have pattern 4 or 5 found before 12 months and who receive radical therapy will be treated as treatment failures. The treatment will be considered a success if the lower bound, rounded to 0.01, is 70% or higher. For a sample size of 44, this means that treatment will be declared a success if 35 or more patients respond.

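### Protocol 10.2.2.5 drops men from the per-protocol set for any later cancer therapy, with no time limit, so the descriptive per-protocol Month 12 response rate is biased upward if failures switch more often than responders

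*Protocol*

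**What the plan says.** Protocol 10.2.2.5 applies to eligible men who "undergo additional radical therapy (surgery or radiation) after the VTP procedure or receive medical therapies (hormone or chemotherapies"). They "will be kept in the intention to treat population but will be excluded from the per protocol population". No visit or date limits the rule.

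Four other places in the Protocol matter:
- Section 10.2.2.4 defines the set ("The per protocol population of efficacy will consist of all patients who" meet the listed criteria) and gives its role: "Descriptive statistics will also be shown using all patients who comply with the study protocol". This is in addition to the intention-to-treat presentation.
- Section 10.3 fixes the outcome: "The primary efficacy variable is the result of the Month 12 biopsy". It names no analysis population for the primary test.
- Section 6.4.11 says that, on the basis of follow-up results or by their own or their clinician's decision, "patients may at any time decide to undergo additional radical therapy".
- Section 5.5.1 sets the length of follow-up: "Subjects will be considered to have completed the study when they have completed all examinations up to and including the Month 60 visit".

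In the SAP, the Efficacy population section reuses the Protocol's per-protocol criteria and adds a requirement for 12-month biopsy data. It does not mention additional therapy. The Primary efficacy analysis section has its own rule for early switches: "Patients who have pattern 4 or 5 found before 12 months and who receive radical therapy will be treated as treatment failures". The missing-data section counts a missing Month 12 biopsy as failure in the primary analysis. The Secondary efficacy analysis section treats radical therapy as a competing risk and then repeats the analysis with it as an event. The heading for changes from the Protocol's planned analysis has no text under it.

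**The concern.** Membership of an analysis set for a Month 12 endpoint should not depend on what happens after Month 12, least of all on something the endpoint itself can trigger. Section 6.4.11 expressly links radical therapy to follow-up results. A correctly treated man with a valid, positive Month 12 biopsy and surgery at Month 14 is a plain failure, yet the Protocol removes him from the per-protocol rate. A man with a clear biopsy and no further treatment stays.

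Two things are at stake. The per-protocol rate reported beside the intention-to-treat rate may look better than the biopsies justify. It can also differ between reports based on the same biopsies, because more men will have switched by Month 60 than by the time the Month 12 data are first analysed. In addition, a reader of both documents cannot tell whether the SAP dropped the exclusion or took it as understood.

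**Working it through.** **The plan's own figure.** The documents give no number for this rule. The nearest figure is the SAP's pass mark of 35 of 44 (one-sided 90% lower bound, rounded to 0.01, at least 70%). With the exact (Clopper-Pearson) bound, 35/44 gives 0.696, which rounds to 0.70, and 34/44 gives 0.672, which rounds to 0.67. The mark of 35 is reproduced.

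**Inputs.** 44 evaluable men, a 70% null rate and an assumed true rate of 83.6% (Protocol 10.1; SAP, Planned sample size). The documents do not say how many men switch, so I let two shares vary:
- f: share of Month 12 failures who later have additional cancer therapy.
- g: share of Month 12 responders who do.

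**Formula.** With r the Month 12 response rate among all men otherwise eligible for the set,

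per-protocol rate = r(1 − g) / [r(1 − g) + (1 − r)(1 − f)].

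This equals r when f = g, exceeds r when f > g, and falls below r when f < g. The direction of bias depends only on which group switches more.

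**Expected per-protocol rate.**

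| r | f | g | Calculation | Rate |
|---|---|---|---|---|
| 70% | 25% | 0 | 0.70 / (0.70 + 0.30 × 0.75) | 75.7% |
| 70% | 50% | 0 | 0.70 / (0.70 + 0.30 × 0.50) | 82.4% |
| 70% | 75% | 0 | 0.70 / (0.70 + 0.30 × 0.25) | 90.3% |
| 70% | 50% | 10% | 0.63 / (0.63 + 0.15) | 80.8% |
| 70% | 50% | 50% | 0.35 / (0.35 + 0.15) | 70.0% |
| 83.6% | 50% | 0 | 0.836 / (0.836 + 0.164 × 0.50) | 91.1% |

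**Worked counts.** Take 44 men with 34 responders and 10 failures, so 34/44 = 77.3%.
- 2 failures switch, no responders: 34/42 = 81.0%.
- 4 failures switch, no responders: 34/40 = 85.0%.
- 4 failures and 4 responders switch: 30/36 = 83.3%.
- 5 of 10 failures and 17 of 34 responders switch (half of each): 17/22 = 77.3%, no change.

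**Protocol and SAP side by side.**

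| Situation | Protocol per-protocol set | SAP efficacy population |
|---|---|---|
| Pattern 4 or 5 found before Month 12, then radical therapy | Excluded | Failure |
| Positive Month 12 biopsy, then radical therapy | Excluded | Failure by his biopsy; no exclusion stated |
| Additional therapy before Month 12 for another reason, no Month 12 biopsy | Excluded | Failure under the missing-biopsy rule, but the population definition requires biopsy data |

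The first row is the only case where the SAP has an explicit rule for the switch and it differs from the Protocol's. In the second row the SAP is silent on the therapy, and the biopsy decides.

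**The case against.** The strongest reply is that no decision rests on the affected set. The intention-to-treat set keeps these men, and the Protocol shows per-protocol results only as additional descriptive statistics. The SAP runs its efficacy analyses on a population that does not repeat the exclusion and that requires major deviations to be adjudicated before the 12-month biopsy, so surgery at Month 14 cannot later become a major deviation. All of this stands, and it limits the reach of the point.

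A reader might infer more in four ways, and the documents do not support them:
- **That the rule could turn a failed trial into a success.** Removing 2 of the 10 failures in the example lifts the one-sided 90% exact bound from 0.672 to 0.709. But that applies the SAP's bound to the Protocol's set, a test in neither document. At the Protocol's one-sided 5%, the bound for 34/42 is about 0.68; 34/40 gives about 0.73, but no per-protocol test is planned.
- **That Protocol and SAP treat every switch in opposite ways.** The explicit conflict covers only switches before Month 12 after pattern 4 or 5.
- **That almost only failures are removed.** Success means no grade 4 or 5, so men with residual 3+3 disease are responders and may also choose treatment. A rate near 100% would need nearly all failures to switch.
- **That the primary result drifts until Month 60.** The SAP bars further primary-endpoint analysis once the Month 12 result is published. The drift concerns the Protocol's per-protocol table.

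What does not stand is the idea that the rule is harmless. The Protocol calls this the per-protocol population of efficacy, Protocol 10.3 names no population for the test, and the SAP's only efficacy population is built from the same criteria with no note that the exclusion was dropped.

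**Conclusion.** The rule is wrong as written. It makes per-protocol membership depend on an event that can follow from the Month 12 outcome, at any time up to Month 60. The descriptive per-protocol Month 12 rate is biased upward whenever failures switch more often than responders. That is plausible given section 6.4.11, but the documents do not quantify it. In the example the shift is 7.7 percentage points (77.3% to 85.0%) if 4 of 10 failures and no responders switch. At a true rate of 70% the expected figure is 75.7% to 90.3% as f runs from 25% to 75% with g = 0. The rate also depends on the data cut.

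The intention-to-treat results are not affected. The SAP's 35-of-44 decision is not affected unless Protocol 10.2.2.5 is read into the SAP efficacy population. This is a should-fix for a supportive analysis and for an undeclared difference between the two documents; it does not overturn the primary decision rule.

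**What to change.** In Protocol 10.2.2.5, replace the per-protocol exclusion with wording to this effect: additional prostate cancer therapy after VTP is not a reason for exclusion from the per-protocol set for the Month 12 endpoint. A man whose Month 12 biopsy precedes the therapy is classified by that biopsy. A man who starts such therapy before his Month 12 biopsy is kept and counted as a failure.

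The last sentence agrees with the SAP's rule for pattern 4 or 5 followed by radical therapy and with its missing-biopsy rule. It goes further for men who switch early for another reason and are still biopsied, a case for which neither SAP rule is written, so that choice should be stated openly.

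In the SAP's Efficacy population section, state that additional therapy is not grounds for exclusion and that the 12-month biopsy data requirement does not remove these men. Record the difference from the Protocol under the SAP heading for changes from the planned analysis.

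The cost is a few sentences in each document. No new data are needed, and patient management does not change. The downside for the sponsor is that the per-protocol rate is likely to be less favourable.

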10.3 Analysis of primary endpoint

The primary efficacy variable is the result of the Month 12 biopsy, in which success is defined by absence of detectable Gleason grade 4 or 5 prostate cancer in any given biopsy.

The primary endpoint will be analysed as a dichotomous outcome, i.e., success (absence of any histology result positive for Gleason 4 or 5 prostate cancer at 12 months) or failure (presence of at least one result positive for Gleason grade 4 or 5 prostate cancer at 12 months).

A descriptive analysis of the month-3 biopsies will be conducted.

10.4 Secondary efficacy endpoints

10.4.1 Definitions

Secondary endpoints are defined as:

- Binary response to treatment defined as the absence of any Gleason grade 4 or 5 biopsy on or before months 24, 36, 48 and 60. If a subject is retreated following a positive biopsy at 3 months and subsequent biopsy shows absence of Gleason grade 4 or 5, the subject will be considered to have responded;
- Binary response to treatment defined as the absence of any Gleason grade 4 or 5 biopsy on or before months 12, 24, 36, 48 and 60 in the treated lobe. If a subject is retreated following a positive biopsy at 3 months and subsequent biopsy shows absence of Gleason grade 4 or 5, the subject will be considered to have responded;

Samples obtained from prostate biopsy procedures will undergo routine processing and examination by the department of pathology at the treating institution. Absence of any Gleason pattern 4 or 5 prostate cancer will be considered negative as will the findings of atypia or prostatic intraepithelial neoplasia.

- Binary response to treatment defined as the absence of any prostate cancer on biopsy on or before months 3, 12, 24, 36, 48 and 60. If a subject is retreated following a positive biopsy at 3 months and subsequent biopsy shows absence of any cancer, the subject will be considered to have responded;;
- Binary response to treatment defined as the absence of any prostate cancer on biopsy on or before months 3, 12, 24, 36, 48 and 60 in the treated lobe. If a subject is retreated following a positive biopsy at 3 months and subsequent biopsy shows absence of any cancer, the subject will be considered to have responded;

Samples obtained from prostate biopsy procedures will undergo routine processing and examination by the department of pathology at the treating institution. Absence of gradable prostate cancer will be considered negative as will the findings of atypia or prostatic intraepithelial neoplasia.

- Changes in biopsy result between 3, 12, 24, 36, 48 and 60 months after the procedure.

Biopsy results obtained at 3 , 12, 24, 36, 48 and 60 months will be compared in each patient to look for change in pathologic findings of gradable cancer between the time points.

- Patients' reported outcome measures (PROMs) impairment: urinary symptoms using IPSS and erectile functions using IIEF prior to treatment beginning and then 1, 3, 6, 12, 24, 36, 48 and 60 months after completing treatment

Quality of life is assessed using validated questionnaires. The IPSS comprises seven questions on the urinary symptoms plus one general question about the QOL related to urinary symptoms, whereas the IIEF comprises 15 questions. For both questionnaires, patients self-rate their responses: for the IPSS, using a six-point scale where 0 indicates 'none' or 'normal', whereas 5 indicates the worst response; for the IIEF, using a five- or six-point scale where 0 indicates 'no sexual activity', and 5 indicates the best response (questions 1 to 10), or where 1 indicates the worst response and 5 the best response (questions 11 to 15).

- Rate of adverse events following treatment

As described in section 9.1, adverse events will be recorded and reported descriptively. Events will be annotated and graded according to National Cancer Institute Common Toxicity Criteria version 4.03.

- Severe prostate cancer-related events: cancer extension to T3, metastasis or prostate cancer-related death

Stage progression to T3 disease (extracapsular extension or seminal vesical invasion), metastasis or cancer-related death will be assessed based on tissue confirmation with biopsy or post-mortem evaluation. Radiographic evidence of suspicious findings will not be utilized unless confirmed with tissue sampling.

- Use of secondary cancer therapies following VTP treatment

Patients who proceed to additional therapies for prostate cancer treatment such as radiation, surgery, hormone or chemo therapies will be documented. Adjunctive surgical or medical therapies that are not intended as cancer treatments but for management of post-treatment related events will be recorded under adverse event reporting and graded appropriately.

- Serum PSA measurements in ng/mL.

Patients blood will be drawn and PSA level determined at 1, 3, 6, 12 months and annually thereafter. Changes from baseline will be determined.

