This is a single center, single-arm, open-label, 60-month follow-up phase IIb clinical trial. Men with localized prostate cancer will receive TOOKAD® Soluble VTP under general anesthesia. Prior to the TOOKAD® Soluble VTP, patients will undergo routine ultrasound examination in the operating room for morphometric description of the prostate and to facilitate accurate treatment guidance for the treatment with TOOKAD® Soluble VTP. Treatment will then be applied to the prostate gland as a hemiablation procedure designed to destroy the lobe of the prostate gland that contains the Gleason score 7 (3+4) cancer. Afterwards, patients will be followed for 5 years (60 months) with clinical evaluation, questionnaires on QOL, erectile and urinary functions, and PSA testing. In addition, treatment outcomes will be assessed based on prostate biopsy results at 3, 12, 24, 36, 48 and 60 months after the TOOKAD® Soluble treatment. All patients will undergo biopsy at 3 and 12 months. Thereafter, biopsy will be performed for cause per institutional standards. If the Month 3 biopsy is positive for any cancer, patients will be allowed a single re-treatment by TOOKAD® Soluble VTP to one or both lobes. However, patients with evidence of clinical deterioration on the same side such as worsening Gleason score, increased core involvement with cancer tumor grades on the 3-month biopsy and/or rising PSA will be withdrawn from the study and proceed with standard care. In addition, patients who experience treatment related Grade 3-4 adverse events during their first treatment will not be re-treated at month 3 and will be proceed with standard care if the month-3 biopsy contains cancer, on the same or contralateral side.

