## **Endpoints**

### **Primary endpoint**

The primary efficacy variable is the result of the Month 12 biopsy, in which success is defined by absence of detectable Gleason grade 4 or 5 prostate cancer.

The primary endpoint will be analysed as a dichotomous outcome, i.e., success (absence of any histology result positive for Gleason 4 or 5 prostate cancer at 12 months) or failure (presence of at least one result positive for Gleason grade 4 or 5 prostate cancer at 12 months).

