### **Secondary efficacy analysis**

#### **Biopsy results**

Biopsy results at each follow-up (3, 12, 24, 36, 48 and 60) for each definition of positive biopsy will be given as cumulative frequency, along with 95% C.I., with radical therapy as a competing risk. The alternative definitions of positive biopsy are:

1. Presence of any pattern 4 or 5 disease (primary endpoint)
2. Presence of cancer of any grade
3. Presence of any pattern 4 or 5 disease in the treated lobe
4. Presence of cancer of any grade in the treated lobe

Analyses will be repeated with radical treatment counted as an event. As retreatment at 3 months is allowed, 3 month results will be treated as a binary endpoint with 95% C.I. presented in a table.

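### Protocol 10.4.1 scores two any-cancer secondary endpoints on gradable cancer only, so carcinoma without a Gleason grade would count as no cancer (minor; descriptive endpoints only)

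*Protocol*

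**What the plan says.** Protocol section 10.4.1 sets out the biopsy-based secondary endpoints in two pairs, each followed by its own scoring sentence.

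- The grade 4 or 5 pair is scored thus: "Absence of any Gleason pattern 4 or 5 prostate cancer will be considered negative as will the findings of atypia or prostatic intraepithelial neoplasia".
- The any-cancer pair (whole gland and treated lobe) opens with "Binary response to treatment defined as the absence of any prostate cancer on biopsy on or before months 3" and continues through Month 60. Its scoring sentence is "Absence of gradable prostate cancer will be considered negative as will the findings of atypia or prostatic intraepithelial neoplasia".
- The change-in-biopsy endpoint compares results within each patient to "look for change in pathologic findings of gradable cancer between the time points".

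The SAP keeps the any-cancer endpoints in its list of secondary endpoints without the word *gradable*. Under Biopsy results, its second definition of a positive biopsy is "Presence of cancer of any grade", and the fourth is the same for the treated lobe.

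The re-treatment provision in the Protocol synopsis uses the broader term: "If the Month 3 biopsy is positive for any cancer, patients will be allowed a single re-treatment".

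Protocol section 7.1 requires the pathology report to state which cores contain cancer, and how much, as items separate from the Gleason grading.

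**The concern.** An endpoint and the rule that scores it should sort every biopsy the same way. Here they do not. *Any cancer* and *gradable cancer* are different sets, and they differ for carcinoma that the pathologist reports without a Gleason grade. The disagreement runs in one direction: the rule can only turn a non-response into a response.

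At stake is the meaning of the reported any-cancer response rates, whole gland and treated lobe, and of the within-patient change comparison. The same Month 3 biopsy could also be recorded as positive for any cancer under the re-treatment provision and as negative for the Month 3 endpoint.

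**Working it through.** **1. One case, followed through each place.** Take a biopsy with carcinoma in one core, no Gleason grade assigned, and no other cancer.

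| Place | Classification of this biopsy |
|---|---|
| Protocol 10.4.1, any-cancer endpoint text | Non-response |
| Protocol 10.4.1, scoring sentence for that endpoint | Negative, hence response |
| Protocol 10.4.1, change-in-biopsy comparison | Not counted as a finding |
| SAP, secondary endpoint text | Non-response |
| SAP, Biopsy results, definitions 2 and 4 | Probably positive, but ungraded carcinoma is not mentioned |
| Protocol synopsis, re-treatment provision | Positive for any cancer |

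The first two rows contradict each other within one section. The SAP leans towards the endpoint text but does not settle the case.

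**2. Could *gradable* serve only to set carcinoma apart from atypia and intraepithelial neoplasia?** Three features of the text count against it.

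- The same sentence already classes those two findings as negative in a separate clause, so the word would be redundant.
- The parallel sentence for the grade 4 or 5 endpoints disposes of the same two findings without it.
- The word returns in the change-in-biopsy sentence, where neither finding is mentioned.

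**3. Can the case occur in the data?** Yes. Section 7.1 records presence and extent of cancer by core separately from grade, so a core with cancer and no grade can be represented.

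**4. Size.** The plan gives no figure to reproduce on this point and no rate of ungraded carcinoma, so the number of patients is an assumption.

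- n = 44 evaluable patients (Protocol 10.1; SAP, Planned sample size).
- k = patients whose only cancer finding up to the time point is ungraded carcinoma; assumed range 0 to 4.
- Shift in response rate = 100 × k / n percentage points.

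| k | Calculation | Shift (points) |
|---|---|---|
| 0 | 0/44 | 0 |
| 1 | 1/44 | 2.3 |
| 2 | 2/44 | 4.5 |
| 3 | 3/44 | 6.8 |
| 4 | 4/44 | 9.1 |

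These are shifts in a simple proportion. The SAP reports follow-up biopsy results as cumulative frequencies with radical therapy as a competing risk, so the shift at later visits would also depend on who is still under observation. A patient who has graded cancer in another core, or at a later biopsy within the period, is positive under either rule and does not enter k.

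**The case against.** The strongest reply has four parts.

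- Protocol 10.2.1 leaves analysis detail to the SAP, which does not carry over *gradable*. Its phrase is most naturally read as cancer regardless of grade.
- Neither document says that carcinoma after this treatment is ever reported without a grade, how often, or in which lobe. The true count may be zero.
- The affected endpoints are descriptive (Protocol 3.3 and 10.4.2), with no test or success threshold, so no trial conclusion depends on them.
- Section 7.1 captures the data needed to identify such cases.

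Most of this stands, and it makes the point a minor one. It does not remove the contradiction in 10.4.1, and the SAP's wording does not clearly cover cancer that has no grade.

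A reader might go further and infer that ungraded carcinoma is scored as a primary success. The *gradable* sentence does not support that, because it belongs to the any-cancer pair alone. The primary endpoint is defined separately, in Protocol 10.3 and in the SAP, where "success is defined by absence of detectable Gleason grade 4 or 5 prostate cancer". Both definitions rest on Gleason grade or pattern 4 or 5 and do not use *gradable*. Both documents are silent on ungraded carcinoma at Month 12, and silence is not a rule that counts it as success. Scoring it as failure would alter a prespecified definition.

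A reader might also note that one patient separates 34/44 (77.3%) from 35/44 (79.5%), the SAP's success count. That is true of any single reclassified patient and shows nothing about this sentence. Nor do the documents support the inference that the effect falls mainly in the ablated lobe.

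**Conclusion.** Wrong as written, but minor. In Protocol 10.4.1 the scoring rule for the two any-cancer secondary endpoints contradicts the endpoints themselves, and the change-in-biopsy comparison carries the same restriction. The SAP omits the restriction without saying how carcinoma with no grade is scored. Any effect favours response. It is 2.3 points per patient at 44 patients, and 0 to 9.1 points over the assumed range of 0 to 4 patients. That range is illustrative, since the documents give no frequency. The finding is confined to descriptive secondary endpoints; the primary endpoint and its success rule are not affected by this sentence.

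**What to change.** In Protocol 10.4.1, reword the scoring sentence for the any-cancer pair so that a biopsy is negative only in the *absence of any prostate cancer, graded or not*. Keep atypia and intraepithelial neoplasia as negative. Delete *gradable* from the change-in-biopsy sentence.

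In the SAP under Biopsy results, add to definitions 2 and 4 that carcinoma without an assigned grade counts as positive. This is an addition, because the SAP does not contain the word to be replaced.

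Leave the primary endpoint definition as it is. At most, report the number of Month 12 biopsies with ungraded carcinoma and add a sensitivity analysis that counts them as failures.

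The cost is a few words in each document. Section 7.1 already records cores with cancer separately from grade, so no new tissue or reader is needed. The downside is that the any-cancer response rates may come out slightly less favourable.
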